	of other subsequent clinical interventions	
	• To evaluate the in-hospital outcomes in patients with COVID-	
	19 pneumonia and hyperinflammation	
	To evaluate the continuous progression of respiratory failure	
	To evaluate the clinical efficacy of mavrilimumab compared to	
	the placebo by clinical severity stratum (i.e. mild vs moderate	
	subgroup)	
	 To evaluate the proportion of patients requiring rescue 	
	medication during the 28-day period	
	 To evaluate change in laboratory parameters through follow 	
	up	
	 To evaluate changes in clinical serological measurements 	
	related to SARS-CoV-2 infection and to mavrilimumab	
	treatment (i.e.ADA) To evaluate changes in the National Farly Warning Score 2	
	• To evaluate changes in the National Early Warning Score 2	
	(NEWS2):	
	- Change from baseline at day 3, 5, 7, 9, 11, 14, 28;	

Protocol design	 Time to clinical improvement defined as a NEWS2 score of 2 or less maintained for at least 24 hours or discharge, whichever comes first To evaluate the variations in radiological findings in patients that underwent a repeated radiological evaluation, comparing those treated with mavrilimumab to those receiving placebo To evaluate the safety of mavrilimumab in patients with COVID-19 pneumonia: Number of participants with treatment-related side effects, serious adverse events, clinically significant changes in laboratory measures and vital signs This study is a prospective, phase II, multi-center, randomized, double-blind, placebo-controlled trial to evaluate the efficacy and
	safety of mavrilimumab in hospitalized patients with acute respiratory failure requiring oxygen supplementation in COVID-19 pneumonia and a hyper-inflammatory status. The study will enroll patients to mavrilimumab or placebo, in addition to standard of care per local practice, which may include but not limited to anti-viral treatment, hydroxychloroquine, low-dose corticosteroids (≤ 15 mg of prednisone or equivalent) and/or supportive care. The total trial duration will be 12 weeks after initial mavrilimumab or placebo dose. Safety will be closely monitored by a dedicated external data safety monitoring board (DSMB) at regular intervals during the study.
Study population	Approximately 50 patients with diagnosed COVID-19 pneumonia and hyperinflammation will be randomized to mavrilimumab or placebo in a 1:1 ratio

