3.2 Secondary objectives and secondary endpoints

Secondary objective	Secondary endpoints
To evaluate clinical outcomes using the 7-point ordinal scale (APPENDIX 1) in patients with COVID-19	- Proportion of responders at day 7, 14, and 28 based on the 7-point ordinal scale. Response is defined as a 7-point ordinal scale of 3 or less, i.e. no supplemental oxygen
	 Time to response, defined as time from date of randomization to the date with a 7-point ordinal scale of 3 or less, i.e. no supplemental oxygen
	- Proportion of patients with at least two-level improvement in clinical status at day 7, 14, and 28
	- Baseline change of clinical status to day 7, 14, and 28
To evaluate the time to disappearance of fever if present at baseline	Time to resolution of fever (for at least 48 hours) in absence of antipyretics, or discharge, whichever is sooner in the 4-week period after

IRCCS San Raffaele Scientific Institute Protocol (v 3.1 – 01 mag 2020)

	study treatment. Resolution of fever is defined as body temperature:
	- ≤36.6°C (axilla) or
	- ≤37.2 °C (oral), or
	- ≤37.8 °C (rectal or tympanic)
	Note: Fever is defined as defined as body temperature > 37.4°C [axilla], or > 38.0 °C [oral], or >38.4°C [rectal or tympanic].
To demonstrate the potential benefit of mavrilimumab in reducing the case fatality rate over 4 weeks among patients with COVID-19 pneumonia and hyperinflammation regardless of other subsequent clinical interventions	COVID-19-related death during the 4-week period after study treatment (in hospital and overall)
To evaluate the in-hospital outcomes in patients with COVID-19 pneumonia and hyperinflammation	Proportion of hospitalized patients who died or required mechanical ventilations (WHO Categories 6 or 7) by day 14
To evaluate change in laboratory parameters through follow up	Variations of the following serological markers over follow-up:
	- C-reactive protein
	- Ferritin
	- D-Dimer
To evaluate changes in the National Early Warning Score 2 (NEWS2, Appendix 2)	- Median changes of NEWS2 score from baseline at day 7, 14, 28 (or discharge, whichever comes first)
	- Time to clinical improvement (as defined as a NEWS2 score of 2 or less maintained for at least 24 hours or discharge, whichever comes first)

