5.1 Inclusion criteria

Participants eligible for inclusion in this protocol must meet all of the following criteria:

- 1. Adults (≥ 18 years of age)
- 2. Signed informed consent by any patient capable of giving consent, or, when the patient is not capable of giving consent, by his or her legal/authorized representative or according to local guidelines
- 3. Patients clinically diagnosed with SARS-CoV-2 virus by PCR or by other approved diagnostic methodology
- 4. Hospitalized with COVID-19-induced pneumonia evidenced by chest x-ray or CT scan with pulmonary infiltrates
- 5. Patient requiring oxygen supplementation (i.e. with a SpO2 \leq 92% while breathing room air) and having a PAO₂/FIO₂ ratio \leq 300 mmHg
- 6. Lactate dehydrogenase (LDH) > normal range and at least one of the following:
 - fever > 38.0 °C;
 - increased levels of C-reactive Protein (CRP) $\geq 10x$ UNL mg/L (≥ 60 mg/l);
 - increased levels of ferritin $\geq 2.5 \times UNL$ ($\geq 1000 \, \mu g/L$)

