15.2 Appendix 2: National Early Warning Score 2 (NEWS2)

Physiological parameter	3	2	1	Score 0	1	2	3
Respiration rate (per minute)	≤8		9–11	12–20		21–24	≥25
SpO ₂ Scale 1 (%)	≤91	92–93	94–95	≥96			
SpO ₂ Scale 2 (%)	≤83	84–85	86–87	88–92 ≥93 on air	93–94 on oxygen	95–96 on oxygen	≥97 on oxygen
Air or oxygen?		Oxygen		Air			
Systolic blood pressure (mmHg)	≤90	91–100	101–110	111–219			≥220
Pulse (per minute)	≤40		41–50	51–90	91–110	111–130	≥131
Consciousness				Alert			CVPU
Temperature (°C)	≤35.0		35.1–36.0	36.1–38.0	38.1–39.0	≥39.1	

SpO2 = oxygen saturation

The oxygen saturation should be scored according to either the SpO_2 Scale 1 or 2 presented in the table above. The SpO_2 Scale 2 is for patients with a target oxygen saturation requirement of 88%–92% (e.g., in patients with hypercapnic respiratory failure related to advanced lung diseases, such as chronic obstructive pulmonary disease [COPD]). This should only be used in patients confirmed to have hypercapnic respiratory failure by blood gas analysis on either a prior or their current hospital admission.

The decision to use the SpO_2 Scale 2 should be made by the treating physician and should be recorded in the eCRF. In all other circumstances, the SpO_2 Scale 1 should be used.

For physiological parameter "Air or Oxygen?": Any patients requiring the use of oxygen or other forms of ventilation to maintain oxygen saturations and support respiration should be assigned a score of 2.

The consciousness level should be recorded according to the best clinical condition of the patient during the assessment. Patients who are assessed as "Alert" (A) should be assigned a score of 0. Patients assessed as "New Confusion" (C), "Responsive to Voice" (V), "Responsive to Pain" (P), or "Unconscious" should be assigned a score of 3.

Scores should be assigned for respiratory rate, systolic blood pressure, pulse, and temperature according to the table above.

NEWS2 values will be calculated electronically throughout the study based upon entry of vital sign parameters by the investigator in the appropriate eCRF.

Reference

Royal College of Physicians. National early warning score (NEWS) 2. Standardizing the assessment of acute-illness severity in the NHS. London: RCP, 2017.

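### The NEWS2 time-to-clinical-improvement endpoint can count an unchanged, oxygen-dependent patient as improved, because its threshold equals the lowest NEWS2 attainable on oxygen

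*Protocol*

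**What the plan says.** Protocol section 3.2 defines the endpoint as a "NEWS2 score of 2 or less maintained for at least 24 hours or discharge, whichever comes first". The synopsis gives the same rule: "Time to clinical improvement defined as a NEWS2 score of 2 or less", held for 24 hours, or discharge. Neither place sets a starting score, a required change or a condition on respiratory support.

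Appendix 2 (section 15.2) fixes the scoring. For the air-or-oxygen item, patients "requiring the use of oxygen or other forms of ventilation to maintain oxygen saturations and support respiration should be assigned a score of 2", whatever the type or intensity of support. Saturation is scored on Scale 2 only in confirmed hypercapnic respiratory failure; "In all other circumstances, the SpO_2 Scale 1 should be used".

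Eligibility (section 5.1) begins with "Patient requiring oxygen supplementation", shown by a saturation of 92% or less on room air, together with a PaO2/FiO2 of at most 300 mmHg. It also asks for raised LDH "and at least one of the following": fever, CRP or ferritin. Section 5.2 excludes mechanical ventilation at randomization and a PaO2/FiO2 below 100 mmHg. Neither section sets a minimum NEWS2.

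Section 11.2 applies the primary endpoint's method (stratified log-rank test, Cox model) to the other time-to-event endpoints, so this one enters a formal comparison between arms.

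**The concern.** A time-to-improvement endpoint should need a patient to improve. Here the threshold and the scoring table coincide: the points for being on oxygen use up the whole allowance, and a patient whose other items are all normal meets the threshold while still dependent on oxygen. If that patient was already in this state at entry, the endpoint records improvement for a course in which nothing changed.

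Other endpoints in section 3.2 carry a guard against this. The fever endpoint is restricted to patients who have fever at baseline, and the ordinal-scale response requires freedom from oxygen. The NEWS2 endpoint has neither kind of guard. At stake is what a log-rank result or hazard ratio for this endpoint would mean: some events would carry no information about recovery, in a trial of about 50 patients.

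**Working it through.** The protocol states no figure for this endpoint that could be reproduced. The check is to score an eligible patient from the Appendix 2 table.

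**Step 1. Lowest score on oxygen (Scale 1).**

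| Item | Range scoring lowest | Points |
|---|---|---|
| Respiration rate | 12–20 per minute | 0 |
| SpO2, Scale 1 | 96% or more | 0 |
| Air or oxygen | oxygen or other ventilation | 2 |
| Systolic pressure | 111–219 mmHg | 0 |
| Pulse | 51–90 per minute | 0 |
| Consciousness | alert | 0 |
| Temperature | 36.1–38.0 °C | 0 |

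Total = 0 + 0 + 2 + 0 + 0 + 0 + 0 = 2. A search over the table's ranges confirmed 2 as the minimum on oxygen. The endpoint threshold is also 2.

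**Step 2. Can an eligible patient have this profile?**

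- The saturation limit applies on room air only; saturation while on oxygen is not limited.
- Fever is one of three alternatives, so a patient can qualify on CRP or ferritin with a normal temperature.
- No abnormal respiratory rate, pulse, blood pressure or consciousness is required.
- The PaO2/FiO2 window can be met. Assuming a PaO2 of 75–90 mmHg at SpO2 96% (an assumption, not in the documents), FiO2 0.35 gives 75/0.35 = 214 to 90/0.35 = 257, and FiO2 0.60 gives 75/0.60 = 125 to 90/0.60 = 150. All lie between 100 and 300.

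Example: alert, rate 18, pressure 125, pulse 80, 37.5 °C, SpO2 96–98% on oxygen. NEWS2 = 2 at baseline.

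**Step 3. Which kinds of support?** The item does not grade intensity, so the score is the same on conventional oxygen, high flow or non-invasive ventilation. The exclusions do not name the first two. Non-invasive ventilation depends on reading exclusion 2 as invasive only. That reading has support: section 3.2 ties mechanical ventilation to ordinal category 6, section 8.4 puts non-invasive ventilation and high flow in category 5, and Table 1 records non-invasive ventilation from screening.

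**Step 4. When is the event recorded?** The score must be held for 24 hours, and section 8.4 has the parameters recorded once a day. Two consecutive daily scores of 2 suffice, so an unchanged patient becomes an event about one day after baseline.

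**Step 5. How narrow is the profile?** Changing one item of the example at a time:

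| Change | NEWS2 | At threshold? |
|---|---|---|
| SpO2 95% on oxygen | 3 | no |
| SpO2 93% on oxygen | 4 | no |
| Temperature 38.5 °C | 3 | no |
| Pulse 95 | 3 | no |
| Respiration rate 22 | 4 | no |
| Scale 2 patient, SpO2 90% on oxygen | 2 | yes |
| Room air, SpO2 92% | 2 | yes |

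Many hypoxaemic patients will miss the threshold at entry. The first row also shows that, after baseline, a move in SpO2 from 95% to 96% on oxygen takes the score from 3 to 2 with the oxygen need still present.

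**The case against.** The case for leaving the endpoint alone has several parts.

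- **Its own objective is change in NEWS2, not freedom from oxygen.** Oxygen is one of seven scored items, and freedom from oxygen is already covered by the primary endpoint and by the ordinal-scale response endpoints. This stands in part. It is a reason to accept the weaker fix (a baseline condition) and a real cost of the room-air fix. It does not justify counting an unchanged score as improvement, which fails even on the endpoint's own terms.
- **The companion NEWS2 endpoint, change from baseline, does not credit an unchanged patient.** True, but it does not repair the time-to-event endpoint.
- **A statistical analysis plan could handle patients already at the threshold.** It could. The protocol, however, states the event rule in full, in two places, without such a condition. This is a stated rule that gives a wrong result, not a detail left open.
- **The profile is narrow and its frequency unknown.** This stands and limits the weight of the point.

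Three stronger readings are tempting, and the documents do not support them. A reader might infer that events occur at time zero; the 24-hour requirement rules that out, since only the score threshold can be met at baseline. A reader might take the sample-size assumption of 83% versus 40%, a difference of 43 points, and shrink it by the share already at threshold (10%, 20% or 30% would give 38.7, 34.4 or 30.1 points). Those proportions belong to the primary endpoint, the shares have no basis in the documents, and this factor is not the effect on a log-rank test or hazard ratio. A reader might also infer bias toward one arm. Randomization and blinding make such events equally likely in both arms at baseline, and no direction follows from the protocol.

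**Conclusion.** The point holds. As written, the endpoint counts an eligible patient on oxygen with SpO2 of 96% or more and all other items at zero as clinically improved about one day after baseline, with no change in condition. This follows from the scoring table, the endpoint rule and the eligibility criteria alone. The part on non-invasive ventilation additionally assumes that exclusion 2 means invasive ventilation.

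The size cannot be stated from the documents: the share of patients at 2 or below at entry is not given and may be a minority, and the loss for the planned log-rank and Cox analysis is not quantified. The consequence is dilution and loss of meaning in one secondary endpoint. The primary endpoint and the sample size are not touched. The definition is worth correcting because the change is small and uses data already collected.

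**What to change.** Use the same wording in the synopsis and section 3.2. Preferred: count the NEWS2 event only when the score is 2 or less with the air-or-oxygen item at 0 (room air), held for at least 24 hours, and leave the discharge component as it stands. Nobody on oxygen or ventilatory support can then reach the event through the score.

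At minimum: require a baseline NEWS2 above 2, or a fall from baseline, and state how patients already at 2 or below are handled. This removes the unchanged patient, but one who starts at 3 or 4 could still reach 2 while on oxygen.

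One residual gap in the room-air version: SpO2 of 92–93% on room air also scores 2 when the other items are zero. Adding the 94% saturation level already used in the primary endpoint would close it.

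Cost: a change of wording. The item is already recorded daily for NEWS2 during hospitalization, so no new data are needed. Events will be fewer and later, and the room-air version will overlap more with the oxygen-independence endpoints.

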To evaluate the variations in radiological findings in patients that underwent a repeated radiological evaluation, comparing those treated	Variations from baseline to subsequent timepoints (when available) in terms of percentage of lung involvement, modifications in

with mavrilimumab to those receiving placebo

the normal parenchyma, ground glass opacities (GGO), crazy paving pattern, parenchymal consolidations, and evolution towards fibrosis.

Analysis will be centralized and performed by at least two independent radiologists, also by means of the IntelliSpace Portal, version 7 (Philips Medical Systems).

To evaluate safety of mavrilimumab in patients with COVID-19-induced pneumonia and systemic hyperinflammation

Number of patients with treatment-related side effects (as assessed by Common Terminology Criteria for Adverse Event (CTCAE) v.5.0), serious adverse events, adverse events of special interest, clinically significant changes in laboratory measurements and vital signs

To evaluate additional outcomes in patients with COVID-19 pneumonia associated with systemic hyperinflammation

To evaluate additional outcomes in patients with COVID-19 pneumonia associated with systemic hyperinflammation such as:

- the duration of hospitalization (days);
- the need for admission into intensive care unit (ICU) and it median duration, if applicable;
- the incidence and median duration of new mechanical ventilation use during the study, if applicable;
- the continuous progression of respiratory failure as evaluated by the PaO_2/FiO_2 ratio in the 28-day period or until discharge, whichever comes first;
- the proportion of patients requiring rescue medication during the 28-day period, if applicable.

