11.1 Determination of sample size

The sample size estimation for this study is based on the primary efficacy endpoint, time to the absence of need for oxygen supplementation. When use a two-side alpha value of 0.05 and assume the proportions of patients who do not need oxygen supplementation by day 14 are 83% and 40% for mavrilimumab and placebo arms respectively, total 28 events are required to achieve a 90% power using a log-rank test.

Approximately total 50 patients will be randomized with a 1:1 ratio to obtain the total target number of events. Analysis for treatment effect will be based on the evaluable population which includes all subjects who are randomized and receive KPL-301/placebo treatment.

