11.2 Statistical analysis

All efficacy analysis will be done based on the evaluable population.

The primary efficacy endpoint, time to the absence of need for oxygen supplementation will be assessed after all patients have reached day 14, with failure to reach absence of need for oxygen supplementation or death before day 14 considered as right-censored at day 14. Logrank test stratified by randomization stratum respiratory insufficiency status (mild vs moderate) will be done to compare the efficacy between the two treatment arms. Hazard ratio and its 95% CI will be estimated using the Cox proportional hazards model. Kaplan–Meier curves will also be provided for each treatment arm.

Subgroup analysis for the primary efficacy endpoint will be done to evaluate the robustness of the data base on the following baseline characteristics using the same methodology as specified above:

- Age ($<50 \text{ vs. } 50-69 \text{ vs. } \ge 70$)
- Respiratory insufficiency status (mild vs. moderate)

For other time to event endpoints, the same methodology used for the primary efficacy endpoints will be repeated. For binary endpoints, Cochran–Mantel–Haenszel test adjusted by the respiratory insufficiency status will be conducted. For continuous endpoints, ANCOVA will be done with treatment as the independent variable and baseline, baseline by treatment interaction, and baseline respiratory insufficiency status as the covariate.

Other than respiratory insufficiency status, no other randomization strata will be used in the stratified analysis due to the small sample size of this study. For any stratified analyses, if one stratum has ≤ 5 events of interest in a log-rank test or the same response in all patients in a CMH test, the analysis will be done without stratification.

Incidence rate of treatment emergent adverse events will be summarized. Descriptive statistics will be done for other safety assessments.

12. Ethical and legal aspects

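### The ICU-admission and rescue-medication endpoints count a patient who dies without the event the same as one who recovers, so the arm with more such deaths can look better

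*Protocol*

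**What the plan says.** The last row of the table in Protocol Section 3.2 gives additional outcomes. Three concern care that a deteriorating patient may need:

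- ICU: "the need for admission into intensive care unit (ICU) and it median duration, if applicable"
- Ventilation: "the incidence and median duration of new mechanical ventilation use during the study, if applicable"
- Rescue: "the proportion of patients requiring rescue medication during the 28-day period, if applicable"

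None of them says how a patient who dies is classified.

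For binary endpoints, Section 11.2 plans a Cochran–Mantel–Haenszel "test adjusted by the respiratory insufficiency status will be conducted". On the population it says: "All efficacy analysis will be done based on the evaluable population". Section 11.1 defines that population as one that "includes all subjects who are randomized and receive KPL-301/placebo treatment". Patients who die after dosing therefore remain in the denominator.

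The only rule for death in Section 11.2 is the one for the primary endpoint: death before day 14 is censored at day 14, so the patient never reaches the good outcome. The same methodology is carried to the other time-to-event endpoints, but nothing carries it to the binary ones.

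Elsewhere in Section 3.2 the protocol does combine death with an event, once: "Proportion of hospitalized patients who died or required mechanical ventilations (WHO Categories 6 or 7) by day 14".

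**The concern.** For an unfavourable yes/no event, death without the event removes the chance of a yes. If the denominator is all dosed patients and no death rule applies, that patient is scored as a no, which is also the score of a patient who improved and went home. The responder endpoint on the ordinal scale does not have this problem, because death is category 7 and so a non-response. Here the direction is reversed, and death improves the arm's figure.

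This matters if treatment changes mortality, and lowering the four-week fatality rate is one of the stated secondary objectives. Deaths outside ICU are also plausible, since one randomization stratum is patients aged 70 and over. A between-arm difference in ICU or rescue use could then partly reflect a difference in deaths, and could have the wrong sign.

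A smaller gap concerns the ICU endpoint. Section 5.2 excludes patients on mechanical ventilation at randomization but does not exclude patients already in ICU. Ventilation is specified as new use; ICU admission is not.

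**Working it through.** **The plan's own figure.** The protocol gives no rate, power or event count for these endpoints. Its one design figure, 28 events for the primary log-rank test, reproduces: hazard ratio = ln(1 − 0.83)/ln(1 − 0.40) = 3.47, and Schoenfeld's formula at two-sided 0.05 and 90% power gives 28. It has no bearing on the present point.

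**How a death is scored, by endpoint.**

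| Endpoint (Section 3.2) | Death without the event |
|---|---|
| Responder, ordinal scale 3 or less | Unfavourable (category 7) |
| Death or ventilation by day 14 | Unfavourable (in the composite) |
| COVID-19-related death, 4 weeks | Unfavourable, if COVID-19-related |
| ICU admission | No rule; a non-event under Sections 11.1 and 11.2 |
| Rescue medication, 28 days | No rule; a non-event under Sections 11.1 and 11.2 |
| New ventilation during the study | Day-14 composite covers deaths to day 14; no rule after that |

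**Inputs for an illustration.** From the protocol: about 50 patients at 1:1, so 25 per arm. Assumed, because the documents give no such rates:

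- p, the event risk among patients who do not die first, equal in both arms at 20%, 30% or 40%.
- d, the share dying without the event, in arms A and B: 4% vs 12%, 4% vs 20%, and 0% vs 16%. The difference is 8 or 16 percentage points.

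**Formulas.**

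- Endpoint as stated: (1 − d) × p. Difference B − A = −p × (dB − dA).
- Event or death: d + (1 − d) × p. Difference B − A = (1 − p) × (dB − dA).

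**One case in full**, p = 30%, deaths without the event 1 of 25 (4%) vs 5 of 25 (20%):

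- As stated: A = 0.96 × 0.30 = 28.8%; B = 0.80 × 0.30 = 24.0%. B looks 4.8 points better.
- Event or death: A = 4.0 + 28.8 = 32.8%; B = 20.0 + 24.0 = 44.0%. B is 11.2 points worse.

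**Over the range** (B − A, percentage points; negative means B looks better):

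| p | dB − dA | As stated | Event or death |
|---|---|---|---|
| 20% | 8 | −1.6 | +6.4 |
| 20% | 16 | −3.2 | +12.8 |
| 30% | 8 | −2.4 | +5.6 |
| 30% | 16 | −4.8 | +11.2 |
| 40% | 8 | −3.2 | +4.8 |
| 40% | 16 | −6.4 | +9.6 |

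With equal p the two signs are always opposite, because p and 1 − p are both positive. In patients, the false advantage is 0.016 × 25 = 0.4 to 0.064 × 25 = 1.6 per arm of 25.

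Equal p is itself an assumption. With deaths of 4% vs 20% and p = 30% in A, the stated endpoint shows no difference when p in B is 0.288/0.80 = 36%. Arm B could therefore have both more deaths and a higher event risk and still look no worse.

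**The case against.** The strongest reply is that the reading rests on silence. Nowhere does the protocol call death a good outcome. Only the rescue item is worded as a proportion, all three sit in an open list of additional outcomes, and an analysis plan not shown here could add a death rule. That stands in part: the yes/no reading of ICU admission is an inference. But the endpoints are fixed in the protocol without death, and the population and test that it names do lead to this scoring.

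Second, the trial as a whole is not blind to deaths. They count against an arm in the four-week mortality endpoint, in the ordinal-scale endpoints and in the day-14 composite. This stands. A reader might infer that excess ward deaths would go unnoticed, or that preventing them would earn no credit; that is true only inside the ICU and rescue comparisons. It also means ventilation is largely covered.

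Three further inferences are tempting and not supported.

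- That rescue will often come too late because the promoter must approve it. The synopsis and Section 6.3 attach approval to investigational COVID-19 treatments, but state no such condition for systemic corticosteroids used as rescue.
- That Table 1 shows patients in ICU at baseline because it marks ICU days on the dosing day. The same column marks days on mechanical ventilation, although ventilated patients are excluded. A mark denotes a data field, not a baseline state.
- That the distortion is large. Suppose rescue-or-death is 40% in both arms, made up of 20% rescued plus 20% dead without rescue in one and 32% plus 8% in the other. At 25 per arm, the stated proportion then favours the arm with more unrescued deaths in about 79% of simulated trials and is nominally significant in about 17% (pooled z test, not the planned CMH). Those results follow from the chosen split. Section 5.2 excludes ventilated patients, those with PaO2/FiO2 below 100 and those expected to die within 24 hours, and nothing in the documents supports 20% unrescued deaths.

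Finally, resource use read beside mortality is a legitimate question, and cumulative incidence with death as a competing event, shown with all-cause death, would be another acceptable form. Both points stand. They are reasons to keep the components visible, not to test them alone.

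**Conclusion.** The point holds for ICU admission and rescue medication, and for new ventilation only after day 14. As written, a death without the event is scored like a recovery, and a difference in such deaths can reverse the direction of the comparison.

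The size cannot be computed from the documents. Under the neutral assumptions above, the arm with more deaths gains 1.6 to 6.4 points on the stated endpoint and is 4.8 to 12.8 points worse on event-or-death. The direction follows from the definitions when event risk is equal in patients who do not die first; the size depends on the assumed rates. If treatment also changes that risk, the net effect could go either way.

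These are lower-tier secondary outcomes. The primary analysis is unaffected, and the mortality and ordinal-scale endpoints remain as a check. The change is worth making because it is cheap and prevents a misleading result, not because the trial's main conclusion depends on it.

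**What to change.** In Section 3.2:

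- Define ICU admission or death, and rescue medication or death, both by day 28 with death from any cause. The existing mortality endpoint counts COVID-19-related deaths only.
- Extend the existing death-or-ventilation endpoint to day 28, alongside day 14.
- For the ICU endpoint, count only new admissions after dosing.

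In Section 11.2, state that these are analysed in the protocol's evaluable population with the planned CMH test. Report the ICU, ventilation and rescue proportions and the deaths descriptively by arm.

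The cost is a few lines of text. Table 1 already provides for vital status, ICU days, ventilation days and concomitant medication, so no new data are needed and no clinical rule changes. The drawback is a composite that mixes outcomes of different severity; the component table lets the reader see which one drives the result.
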